## 7.10 Analysis of safety (key secondary endpoint)

### 7.10.1 Adverse events

AEs relating to mothers (study subjects) will be coded using the latest available version of MedDRA. An overall summary table will be provided showing the number and percentage of subjects, within the SAF analysis set, with any:

- Treatment-emergent adverse event (TEAE)
- Severe TEAE
- Treatment-emergent SAE
- Vaccine related TEAE

- Vaccine related severe TEAE
- Treatment-emergent vaccine related SAE
- TEAE leading to withdrawal
- TEAE with outcome death

The frequencies of the following key secondary safety endpoints will be tabulated in descriptive frequency tables:

- Solicited injection site events following the vaccinations
- Solicited systemic AEs following the vaccinations
- All AEs following the vaccinations

Treatment emergent AEs will be tabulated by system organ class and preferred term and treatment using the latest MedDRA coding.

All treatment emergent events will be listed. Non-treatment emergent events (if any) will be listed separately.

AEs in babies will be analysed and presented similarly to AEs in mothers, described above.

With respect to the babies, the following set of safety information will likewise be tabulated in descriptive summary tables (BSA analysis set):

- Gestational age
- Weight
- Length
- Head circumference
- Apgar score at 1, 5 and 10 minutes
- Developmental milestones at 6 months of age

### **7.10.2 Safety laboratory assessments, urinalysis and vital signs**

Treatment groups are compared as regards safety laboratory tests, urinalysis, and vital signs measurements, presenting severe (grade 3) or greater results, according to the FDA toxicity grading scale, as well as clinically significant results, as assessed by the investigators, and evaluation of changes since baseline, as applicable, using descriptive statistics. More details will be included in the SAP.

### **7.11 Analysis of immunogenicity (exploratory endpoints)**

The exploratory immunogenicity analysis for this study will be described in a separate statistical analysis plan under the responsibility of the researchers in MinervaX AB, Sweden.

## 7.12 Interim analysis

An early analysis of data available up to, and including, Visit 8 will be performed based on unblinded cleaned data. The analysis will include the primary immunological endpoint for IgG antibodies specific to the AlpN proteins in cord blood, the key secondary safety endpoints in all study participants (maternal participants and babies), and the secondary immunological endpoint for IgG antibodies specific to the AlpN proteins in maternal blood.

The early analysis will be conducted by an unblinded team within the CRO and the sponsor. Separate teams within the CRO and the sponsor will remain blinded until the end of the study to ensure further study execution in a blinded manner. Investigators, and site personal and study participants will remain blinded until the end of the study.

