Based on the immunogenicity results of the IgG concentrations specific to the AlpN proteins in cord blood at delivery, as well as the safety results, one of the vaccination regimens will be selected for phase III development. To inform decisions on the vaccination regimen selection as well as the design of a long-term follow-up study, an early analysis of study data for the primary and key secondary endpoints available up to 72 hours after delivery (Visit 8) will be performed. Early analysis of these data will allow to advance the clinical development plan for the GBS-NN/NN2 vaccine, which will help to address the unmet medical need for GBS vaccination during pregnancy.

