**Footnotes**

- a. Gestational age and gender.
- b. Apgar score at 1, 5 and 10 minutes if available (available scores will be collected, 'not recorded' will be an option).
- c. Heart rate (actual, not Apgar score).
- d. Cord blood or infant blood (heel prick or venous sample) within 72 hours of birth.
- e. Heel prick or venous sample.
- f. Age-appropriate developmental milestone check.
- g. After the first 28 days of age, only MAAEs, AEs of special interest (AESI), e.g., GBS disease and abnormal development according to developmental milestones, or SAEs, and CMs prescribed for such events until 180 days of age.
- h. Visit 9-11 may be performed as home visits.

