## 6.4 Reporting of adverse events including SAEs, MAAEs and AESIs

AEs will be reported in the eCRF pages from informed consent until the subject has completed/is withdrawn from the study (including any follow-up period), see details in Table 2 for mothers and Table 3 for babies.

Adverse events identified from the e-diaries will be transferred to the AE form in the eCRF, if they meet the following criteria:

- Any unsolicited AE
- Solicited local or systemic reaction to be assessed for the subject's withdrawal from study or study vaccine
- Solicited local or systemic reaction, rated by the subjects in the eDiary, categorized as severe
- Solicited local or systemic reaction lasting beyond 7 days from the day of vaccination
- Solicited local or systemic reaction that meets the definition of a SAE

Solicited local or systemic reactions are per definition regarded as related to the study vaccine, and the intensity is defined as described in section 6.1.

All maternal SAEs, as well as medically attended adverse events (MAAEs) and AEs of special interest (e.g., GBS disease, autoimmune diseases and immune-mediated reactions) will be reported from the day of signing informed consent for study participation and until the end of the study (Visit 11).

All baby SAEs, as well as MAAEs and AESIs (e.g., GBS disease, abnormal development according to developmental milestones), will be reported from birth up to 180 days post-delivery (Visit 11).

All SAEs, and AESIs, occurring from the time of signing the informed consent form until the subject has completed the study will be reported by completing and sending the SAE form (via email, or if required, via fax) to the pharmacovigilance provider (contact details below) within 24 hours of awareness / learning about the event i.e., within 24 hours after the investigator becomes aware that the event meets the protocol definition of a SAE.

SAEs occurring after study termination must be reported if considered related to the study drug.

After the initial SAE report, the investigator is required, proactively, to provide further information regarding the subject's condition.

In case of a fatal or life-threatening suspected unexpected serious adverse reaction (SUSAR), relevant follow-up information should be forwarded immediately.

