## 2.4 Blinding

Each site PI will be able to unblind an individual subject. The blinding should only be broken in case of an emergency, and only if the knowledge obtained through the unblinding is assessed to be needed for the proper treatment or continued safety of the subject experiencing the emergency.

The pharmacovigilance responsible CRO will be able to unblind an individual subject prior to submitting an expedited report of a suspected unexpected serious adverse reaction (SUSAR) to a CA or IEC, if unblinding is required by the CA or IEC.

Whenever possible, the sponsor, MinervaX, should be consulted before the blind is broken by the site.

The unblinding of a subject by the site PI or the pharmacovigilance responsible CRO takes place through the unblinding module in the eCRF, to which the applicable parties will be given access.

If unblinding of a subject has taken place (intentionally or unintentionally), the sponsor must be informed immediately, and be provided with an explanation, and it must be considered to withdraw the unblinded subject from the study.

The information in this section is described in more detail in a study specific blinding manual.

During conduct of the study an unblinded DSMB will work independently from the blinded study team. Likewise, an interim/early efficacy analysis focused on unblinded immunogenicity data, and certain key safety data, will be conducted when Visit 8 has been completed for the last subject (baby). These activities involving unblinded personnel are described in further detail in section 6 below.

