## 6 Interim analyses

There will be blinded, sponsor-internal safety reviews conducted on an ongoing basis as well as recurrent reviews by an unblinded DSMB. The function and responsibilities of the DSMB is documented in the DSMB Charter. The DSMB and the attached independent unblinded statistician and programmer will work in a setup completely separated from the blinded study team.

Unblinded analysis of selected endpoints up to (and including) Visit 8 will be performed based on cleaned data. This analysis (summaries and statistical analysis as described in section 4) will include the primary immunological endpoint for IgG antibodies specific to the AlpN proteins in cord blood, the key secondary safety endpoints in all study participants (maternal participants and babies), and the secondary immunological endpoint for IgG antibodies specific to the AlpN proteins in maternal blood. An overview of the considered objectives, endpoints, and relevant visits is given in Table 5 below.

This analysis will be conducted by an unblinded team within the CRO and sponsor. Separate teams within the CRO and the sponsor will remain blinded until the end of the study to ensure further study execution in a blinded manner. Investigators, and further site personal and study participants will remain blinded until the end of the study. Procedures to ensure that blinded and unblinded personnel remain in their roles are described in a ‘firewall’ charter, an extension of the general blinding plan.

As no hypotheses are tested repeatedly and no early stopping of the trial is envisioned, no multiplicity adjustments related to the early analysis are planned.

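### The early analysis that informs the phase III regimen choice stops safety at each pair's own Visit 8, so later deaths, SAEs and AESIs already reported would not be shown by arm

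*Protocol*

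**What the plan says.** **Purpose.** Protocol 2.5 bases the regimen choice on cord-blood IgG "as well as the safety results, one of the vaccination regimens will be selected for phase III development". It gives the purpose of the early analysis as "To inform decisions on the vaccination regimen selection as well as the design of a long-term follow-up study", using "endpoints available up to 72 hours after delivery (Visit 8) will be performed".

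**Cut.** Protocol 7.12: "An early analysis of data available up to, and including, Visit 8 will be performed based on unblinded cleaned data". SAP section 6: "Unblinded analysis of selected endpoints up to (and including) Visit 8 will be performed based on cleaned data". SAP Table 5 lists maternal safety for Visits 1 to 8 and baby safety, including AEs, for Visit 8 only.

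**Timing.** SAP 2.4 runs the analysis when the last baby has completed Visit 8.

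**Collection after Visit 8.** For babies, all AEs are collected for 28 days. Protocol Table 3, footnote g, then continues: "After the first 28 days of age, only MAAEs, AEs of special interest (AESI), e.g., GBS disease and abnormal development", plus SAEs, until 180 days of age. Mothers are followed for SAEs, MAAEs and AESIs to Visit 11. Protocol 6.4 adds: "All SAEs, and AESIs, occurring from the time of signing the informed consent form until the subject has completed the study will be reported" to the pharmacovigilance provider, within 24 hours of awareness.

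**Who sees later events.** Under SAP section 6 the sponsor's ongoing safety reviews are blinded and the DSMB is unblinded. Protocol 6.7 gives the DSMB the task of recommending continuation, modification or termination of the study and of advising the sponsor on safety. It does not mention regimen choice.

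**The concern.** The cut is set by visit, while the analysis is triggered by the last delivery. Every pair that delivered earlier has gone on being followed. A death, SAE or AESI on day 20 or day 100, already sent to the pharmacovigilance provider, would be left out of the by-arm tables because of the visit it falls after, even though it is known.

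Safety is a stated ground for choosing the regimen. Two of the four regimens start at 22 weeks of gestation, whereas the first vaccine dose in the ongoing pregnancy study is given at 26 to 30 weeks (Protocol 2.4 and 2.6). If the choice is made on the early analysis, those making it would not have had known later serious events set out by arm.

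**Working it through.** The plan gives no figure on this point, so there is none to reproduce. The check has four parts.

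**1. Share of each safety window that falls before the cut**

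| Window | Source | Before the cut |
|---|---|---|
| Baby SAE/MAAE/AESI, birth to day 180 | Protocol 6.4 | 3/180 = 1.7% |
| Baby all AEs, first 28 days | Protocol 4.3.3 | 3/28 = 10.7% |
| Late-onset GBS disease, days 7 to 89 | Protocol 2.1 | none |
| Developmental milestones, first checked at Visit 9 | Protocol Table 3 | none |
| Mother, first dose to 180 days after delivery | 18 weeks = 126 days to delivery (Protocol 4.6.1) | (126 + 3)/(126 + 180) = 129/306 = 42% |

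**2. Follow-up that already exists when the analysis runs**

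The documents do not give the accrual period. Assume that births are uniform over E months (D = 30.4 × E days), that nobody drops out, that the cut is 3 days after the last birth, and that follow-up is capped at 180 days. Age at the cut is then uniform from 3 to D + 3 days.

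- Mean follow-up = D/2 + 3 − (D − 177)²/(2D)
- Share past day 28 = 1 − 25/D; past day 90 = 1 − 87/D; past day 180 = 1 − 177/D
- Share of accrued follow-up lying after day 3 = 1 − 3/mean

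| E (months) | D (days) | Mean (days) | Past day 28 | Past day 90 | Past day 180 | After day 3 |
|---|---|---|---|---|---|---|
| 6 | 182.4 | 94 | 86% | 52% | 3% | 96.8% |
| 12 | 364.8 | 137 | 93% | 76% | 51% | 97.8% |
| 18 | 547.2 | 151 | 95% | 84% | 68% | 98.0% |

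The last column is high almost by construction, because 3 days are set against months. The mean and the shares past days 28 and 90 say more.

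**3. How many late-onset GBS cases could be missed**

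Protocol 2.1 cites 0.49 invasive cases per 1,000 live births, and 205,000 early-onset and 114,000 late-onset cases worldwide.

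- Any onset in 270 babies: 270 × 0.00049 = 0.13 cases
- Late onset: 0.13 × 114/(205 + 114) = 0.13 × 0.357 ≈ 0.05 cases, over all five arms
- At five times that incidence (an assumption): about 0.24 late-onset cases

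**4. Is the gap filled elsewhere?**

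The second DSMB meeting covers 27 births with 28 days of follow-up, and the third falls one year after the first subject's first visit (Protocol 6.7). These reviews serve participant safety. Neither document has them, or any other planned output, give the unblinded sponsor team a by-arm table of events after Visit 8 at the time of the early analysis.

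**The case against.** A uniform Visit 8 cut is a standard choice. It gives each pair complete, cleaned follow-up to the same milestone. It also captures the outcomes closest to vaccination: solicited reactions after all injections, AEs and laboratory tests during pregnancy, gestational age, birth size and Apgar scores. Protocol 2.1 puts 60–90% of early-onset GBS disease on the first day of life, inside the cut. Six-month milestones would be largely immature if births accrue quickly: with 6-month accrual, about 3% of babies are past day 180. All of this stands, and it is why the Visit 8 cut should remain for the other endpoints.

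Four stronger readings are tempting, and the documents do not support them.

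- **That the regimen will be chosen on Visit 8 safety alone.** Protocol 2.5 says that the early analysis informs the decision. It gives no decision date, and follow-up to Visit 11 is still analysed at the end.
- **That the later events are certainly in the database.** Reporting within 24 hours of awareness and the wait for the last baby make this likely. But the amount depends on an unstated accrual period, the expedited route is a form sent to the pharmacovigilance provider, and the later eCRF data may not be clean.
- **That the cut hides a difference in late-onset GBS disease.** With about 0.05 expected cases, there is almost nothing to compare.
- **That late safety goes unwatched.** The DSMB is unblinded, may recommend changes to the study and advises the sponsor. Protocol 6.8 lists a single SAE judged related to vaccination among the events that warrant a halt for DSMB review or early termination.

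What remains is narrow: none of these routes puts known later serious events by arm in front of those choosing the regimen.

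**Conclusion.** The point holds as a cheap improvement. It is not an error or an internal contradiction. Both documents stop safety at each pair's own Visit 8, and neither adds later deaths, SAEs or AESIs to the early analysis.

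Two figures set the size. The cut covers 3 of 180 baby days, which the documents fix, and about 42% of the maternal window, which takes delivery at about 18 weeks after first dose and follow-up to 180 days. The volume of later data at the cut rests on assumed uniform births over 6 to 18 months without dropout. On that basis babies average 94 to 151 days of follow-up, and 52–84% are past day 90.

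The benefit is that no known death, SAE or AESI, of any cause, is missing when the regimens are weighed. The counts will be too small to rank regimens statistically and should not be used that way.

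**What to change.** Add to Protocol 7.12, SAP section 6 and SAP Table 5 a text such as: *All deaths, SAEs and AESIs in mothers and babies reported up to a stated calendar cut-off date, including those after Visit 8, will be tabulated and listed by arm after reconciliation with the pharmacovigilance records. The number of pairs that have reached Visits 9, 10 and 11 and the follow-up time per arm will be shown. The table is descriptive and will be labelled as incomplete follow-up.* Keep the Visit 8 cut for all other endpoints.

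The cost is a short addition to each document, one table with a listing, and some extra reconciliation, since these records will not all have gone through full cleaning. Follow-up will be uneven between early and late enrollees. Randomisation is blocked within site (SAP 2.5), so it should be similar across arms on average, and the follow-up time per arm lets the reader check. Counts will change by the final report. The same unblinded team does the work behind the existing firewall, so the blind is unaffected. No hypothesis test or clinical rule changes.

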## 7.13 Sample size determinations

For the assessment of adequate sample size, data from the finalized phase I study MVX0002 has been considered. In that study, 23 healthy females of childbearing potential were exposed to double vaccination, one month apart, with the vaccine of the present study. The seroprotection levels (%) obtained, as defined by cut-points 0.5, 1.0, 2.0 and 4.0, are shown in the following table.

| Antigen | Cut-point 0.5 | Cut-point 1.0 | Cut-point 2.0 | Cut-point 4.0 |
|---------|---------------|---------------|---------------|---------------|
| Alp1-N  | 100.00        | 95.65         | 95.65         | 86.96         |
| Alp2-N  | 100.00        | 95.65         | 95.65         | 91.30         |
| AlpC-N  | 100.00        | 95.65         | 91.30         | 73.91         |
| Rib-N   | 95.65         | 95.65         | 82.61         | 60.87         |

Although the cord-blood samples of MVX0004 are somewhat different from these samples derived from healthy adults, they are believed to be close enough for an analogy to hold.

Using the antigen-specific expected seroprotection levels corresponding to cut-point = 1  $\mu$ g/ml as basis, the power of the non-inferiority tests described in Section 7.8, should be above 90 % if equal responses in the vaccination groups 1, 2 and 3 are assumed. For higher cut-points (2/4/8) this power will however most likely be smaller, in particular for the IgG corresponding to the Rib-N protein.

## **8 Ethical, legal and GCP aspects**

### **8.1 Declaration of Helsinki and good clinical practice**

The clinical study MVX0004 is planned, conducted and reported in compliance with this protocol, the latest version of the ‘Declaration of Helsinki’, the ‘ICH E6 (R2)’ and ‘Directive 2001/20/EC’ (to be replaced by ‘EU Regulation 536/2014’, when implemented).

### **8.2 Informed consent**

The written subject information and the informed consent form will not be used until approved by the applicable IEC(s) and CA(s). All participants must provide written informed consent.

Potential participants who volunteer for participation in the study will be informed of the aims, methods, anticipated benefits and potential hazards of the study and any possible discomfort it may entail. Information will be given in both oral and written form and in a manner deemed appropriate. Each participant will also be informed of his/her right to withdraw from the study at any time, for any reason.

The participant will be allowed sufficient time to consider the study information. Prior to signing the informed consent form (ICF), the participant will be given an opportunity to discuss any issues concerning the study with site study staff who have suitable knowledge of the study and will have all questions answered openly and honestly.

If the participant is willing to participate in the study, the ICF will be signed and personally dated by the participant and the person taking consent.

The participant will receive a copy of the ICF together with the participant information sheet and the original signed ICF will be retained with the study records at the investigational site. In addition, the actions and completion of the consenting process will be recorded in the participant’s medical record (*i.e.*, source document).

Parental informed consent on behalf of fetus the baby to be born will be given according to national regulations applicable to the sites.

### **8.3 Independent Ethics committee submission and approval**

The study will not be initiated until it has been approved by the applicable IEC(s).

The sponsor, or delegated CRO will, according to applicable guidelines and legislation and in collaboration with the site PIs, prepare a clinical trial application (CTA) to be submitted to the IECs, responsible for the respective investigational sites.

The expected timelines for approval are as given in the current guidelines/regulations (‘Directive 2001/20/EC’ to be replaced by ‘EU Regulation 536/2014’, when implemented) for Denmark, and for the UK, as given in current UK national guidelines/legislation applicable to IECs, and for South Africa as given in current local national legislation applicable to IECs.

## 8.4 Competent authority submission and approval

The study will not be initiated until it has been approved by the applicable CA(s).

The sponsor, or delegated CRO, will prepare a clinical trial application (CTA) to be submitted to the CAs in Denmark, the UK and in South Africa.

## 8.5 Personal data protection and confidentiality

MinevaX' processing of personal data is subject to regulation (EU) 2016/679 of the European Parliament and of the Council of 27 April 2016 on the protection of natural persons with regard to the processing of personal data and on the free movement of such data and repealing Directive 95/46/EC, General Data Protection Regulation (GDPR), Article 6(1)(c) and 9(2)(i), as well as various special legislation and guidelines related to the processing of health information in connection with clinical trials and registration of medicines.

The principal investigator is responsible for keeping a subject identification log of study subjects including personal identity information, e.g., full name, address, personal identification number etc.

The study documents containing personal identity information, e.g., the screening log and the signed informed consent forms, will be kept in a secure place, at the investigational site at all times, and will not be transferred to the sponsor or any third party at any time.

All other study documents, electronic records or labels on biological samples will not contain personal identity information but will identify the study subjects by use of a subject number and is this way pseudonymised (encrypted). Only, through linking the subject number to the screening log (kept in a secure place at the investigational site) the subject can be identified.

MinervaX may transfer or provide access to the personal data to entities located in countries outside the EU/EEA that the European Commission has not found to ensure an adequate level of protection of personal data. MinervaX will strive to ensure that adequate safeguards (contractual or otherwise) are in place (e.g, European Commission standard personal data protection clauses) to protect the privacy of personal data, however, this may not always be possible.

